Secondary objective(s) Safety • To evaluate the time to cardiovascular events of interest in OSA patients exposed to OZAWADE® as per SmPC compared with OZAWADE®-unexposed OSA patients. • To evaluate the time to adverse drug reaction (serious and non-serious) in OSA patients exposed to OZAWADE® as per SmPC compared with OZAWADE® unexposed OSA patients. Exploratory objective(s) **Effectiveness** • To evaluate the effectiveness of OZAWADE® through the Epworth Sleepiness Scale (ESS) when used as per SmPC in patients with OSA. • To evaluate the effectiveness of OZAWADE® through the Maintenance of wakefulness test (MWT) when used as per SmPC in patients with OSA. • To evaluate the effectiveness of OZAWADE® through the Multiple Sleep Latency Test (MSLT) when used as per SmPC in patients with OSA. • To evaluate the effectiveness of OZAWADE® through the Fatigue Severity Scale (FSS) when used as per SmPC in patients with OSA. Adherence • To evaluate the adherence to OZAWADE® when used as per SmPC in patients with OSA. • To evaluate the adherence to continuous positive airway pressure (CPAP) / mandibular advancement devices (MAD), between the group of patients exposed to OZAWADE® and the group of patients not exposed to OZAWADE®. Other To evaluate the reduction of car/traffic accidents. Country(-ies) of study 4 countries: France, Italy, Germany and possibly Netherlands, Belgium or Spain **Author** Study Medical Director **Bioprojet Pharma** Tel: + E-mail address:

This protocol was drafted according to Good Epidemiological Practices

Confidential information

The information contained in this protocol is confidential and is intended for the use of Participating physicians.

This document is the property of Bioprojet pharma and should not be – in whole or in part – transmitted, reproduced, published or used without expressed authorisation of Bioprojet Pharma. The information contained in this protocol is confidential and is intended for the use of participating physicians.

Marketing authorisation holder(s)

Marketing authorisation holder(s)	Bioprojet Pharma
	[name]
	[name]
	France
	Phone: +
	www.bioprojet.com
MAH contact person	
	Regulatory Affairs Director
	Tel: +
	E-mail address:

Participation to the study / Confidential agreement

Information contained in this protocol are confidential and are the property of Bioprojet Pharma.

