9.1. Study design

9.1.1. Overall Design of the Study

This is a prospective, observational, multi-center, open-label, long term, cohort study (OZAWADE® exposed and OZAWADE® unexposed) designed to collect data on the long-term safety of OZAWADE® treatment. This study will be conducted in OSA patients with EDS whose EDS has not been satisfactorily treated by, or who have not tolerated OSA primary therapy. The study will be conducted by physicians specialized in sleep management such as sleep specialists, pulmonologists, cardiologists, otorhinolaryngologist and neurologists.

[figure not shown]
As an observational study, the assignment of the patient to a particular therapeutic strategy should be decided within the current clinical practice and the decision to prescribe OZAWADE® should necessarily precede and be independent of the decision to enrol the patient into the study. OZAWADE® should be prescribed and used based on the routine clinical practice as well as on the individual situation of each patient, according to the approved SmPC.

During the 2-year enrolment phase, 502 patients are planned to be recruited in four to five countries where OZAWADE® is on the market (*i.e.*, France, Germany, Italy and possibly Netherlands, Belgium or Spain), in approximately 8 to 15 centers per country.

Once eligible patients are enrolled, baseline data should be collected. Data collected in the CRF will correspond to data collected in routine practice in the investigating centers.

Patients will be followed-up up to five years, during which time they should be assessed by their treating participating physicians at 6, 12, 24, 36, 48 and 60 months, to follow routine care schedule.

Study visits, procedure and evaluations are summarized in the study flow (Figure 1) and schedule of assessments below (Table 2).

CPAP: Continuous Positive Airway Pressure; EDS: Excessive Daytime Sleepiness; FU: Follow-up; MAD: Mandibular Advancement Device; OSA: Obstructive Sleep Apnoea.

Figure 1: Study Flow.

PASS Protocol [P21-02/OZAWADE]

OZAWADE

Table 2. Schedule of Assessments

	Procedures ¹ /Visits	Inclusion	FU 6 Months	FU Year 1	FU Year 2	FU Year 3	FU Year 4	FU Year 5	End of study
	Visit window		6M [3-9M[12M [9-18M[24M [18-30M[36M [30-42M[48M [42-54M[60M [54-66M[
	Demography: age, gender	X	ē.						
	Profession / Socio-economic status	Х							
Patient interview	Height², weight	Х	Х	Х	X	X	X	X	Х
nten	Waist circumference	X	х	Х	X	X	X	х	Х

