9.7.5. Primary Analyses

The main objective of the study is to demonstrate that OZAWADE® supplementation does not increase CV events compared with control (non-inferiority). The following analysis will be conducted:

The annual CV morbidity incidence will be estimated by the occurrence of CVE per patient per year equivalent to the proportion of patients with at least one CVE.

The CV risk is known to be higher for OSA patient with existing CV history, using or not CPAP, and well-known risk factors: diabetes, cholesterol, weight, hypertension, demographics (age, gender), lifestyle (fitness, alcohol use, smoking habits).

A generalized linear mixed model featuring Poisson regression will be based on a post stratification model based on the following fixed covariates or random effects:

- nCVE_b, prior CV history measured by the number of CV events experienced before baseline, expected as the essential predicting covariates;
- Risk factors (RF): diabetes, cholesterol, weight, hypertension, alcohol use, and smoking habits reported at baseline;
- Demographics: gender, age, country, study center
- Matched classes propensity clusters: the treatment will be non-randomized but determined by the investigator, involving an expected imbalance between groups on baseline conditions. The decision of prescribing a given medicine will be assumed on a set of baseline covariates defined in the statistical plan. As too many covariates are expected, finding sufficient exact matches is unfeasible, and the goal of subclassification is to form matched subclasses (clusters), such that in each the distribution of covariates for the treated and control groups are as similar as possible. The propensity score will be used as the scalar distance with a two-stage algorithm starting with the nearest neighbour matching and optimized by a full matching procedure [39, 40, 41].

The final model is:

CVE ~ $nCVE_b + \Sigma_i RF_i + gender + age + trt + \{country\} + Offset (log-exp) + \{center | country\} + \{cluster\}$

The notation Σ_i RF_i covers the above mentioned considered risk factors. The obvious effect of the exposure duration is measured by the offset of its logarithm. The last fixed factor is the treatment (trt) binary effect (0=control, 1=pitolisant). Country, site effect nested within country, and cluster (matched group) effects will be used as random factors (between {}).

Sensitivity Analysis

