9.9. Limitations of the research methods

The design of this study was carried out in order to limit the major usual biases for this type of study. However, as any observational research this study is subject to risks of bias.

Patient selection bias: selection bias should be taken into account when interpreting the results of the study, especially the limitation on generalizability of study data. It is planned to have a sample of 195 patients exposed to OZAWADE® and 195 not exposed. These results will thus provide a good insight on OZAWADE® data outside the context of an interventional study by providing descriptive data in a real-life context. The

description and follow-up of this subset of patients followed in four countries will be of scientific value. However, to limit selection bias, any physician specialized in sleep medicine who receive, in medical consultation, OSA patients with diagnosis of excessive daytime sleepiness and who are likely to treat them with OZAWADE (sleep specialists, pulmonologists, cardiologists, otorhinolaryngologists and neurologists) will be selected.

Information bias / measurement bias: each subject included in the study has his/her own physician, and therefore, it is expected that information issued from source dossier (i.e. medical file) will be different from a subject to another and may possibly lead to an information and measurement biases. Response and safety assessments may not be uniform. This bias is inherent to the usual physician practice and such study design, and cannot be avoided. To minimize this bias, a training session during on-site study initiation meetings will be provided to all physicians involved in the study, in which clear definitions of the variables measured will be explained.

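### Country is a random factor with only four to five levels, so country confounding is only partly removed from the primary rate ratio; a fixed country term removes it at almost no cost

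*Protocol*

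**What the plan says.** Section 9.7.5 fixes the primary model: "A generalized linear mixed model featuring Poisson regression will be based on a post stratification model", with a log-exposure offset and a binary treatment term. The formula is presented as final, and of its grouping terms the text says: "Country, site effect nested within country, and cluster (matched group) effects will be used as random factors".

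The title table lists "4 countries: France, Italy, Germany and possibly Netherlands, Belgium or Spain". Section 9.1.1 says "502 patients are planned to be recruited in four to five countries", "in approximately 8 to 15 centers per country". Country therefore has four or five levels, while centre has several dozen.

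Section 9.7.5 says that the investigator chooses the treatment and that baseline imbalance is expected. Section 9.2.2.2 applies the recruitment target to the two groups globally, so nothing balances exposed and unexposed patients within a country. The covariates of the propensity score are left to the statistical plan.

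**The concern.** A random intercept treats the country effect as unrelated to the share of exposed patients in that country. It pulls the country estimates toward a common mean, and when the variance is estimated as zero the country term contributes nothing. In a randomized trial stratified by country this would hardly touch the treatment coefficient. Here exposure is a clinical choice and its share can differ freely between countries.

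Recorded CVE rates can differ too. Section 9.3 makes no assessment obligatory. Section 9.3.10 counts QT prolongation as a CVE although ECGs are collected only when available, and it counts new hypertension only where treatment is started or adjusted. Section 9.9 concedes that safety assessment may not be uniform.

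If exposure share and CVE rate are associated across countries, the part of the country effect that is shrunk away stays in the treatment coefficient. The direction matters because the claim is non-inferiority. If low-rate countries have more exposed patients, the rate ratio is biased downward and a false conclusion of no increase in risk becomes more likely.

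**Working it through.** **No plan figure to reproduce.** The public text shows no alpha, margin, event rate or dropout (section 9.5 and Appendix 1 show no calculation), so there is no error rate to rebuild. Everything below that is marked as assumed is mine.

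**Step 1: how well can a country SD be estimated?** Suppose the K country means were known exactly. The 95% limits for the SD, as multiples of the estimate, are √[(K−1)/χ²(0.975; K−1)] and √[(K−1)/χ²(0.025; K−1)].

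- K = 3: 0.52 to 6.3
- K = 4: 0.57 to 3.7
- K = 5: 0.60 to 2.9

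The SD can be estimated, but very imprecisely.

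**Step 2: effect on the non-inferiority test.** Inputs from the protocol:

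- 390 patients (section 9.9: "It is planned to have a sample of 195 patients exposed to OZAWADE® and 195 not exposed")
- four or five countries, with three run as well
- 10 centres per country, or 12 with three countries (section 9.1.1: 8 to 15)
- treatment not randomized

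Assumed:

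- mean follow-up of 4 years (section 9.1.1: "Patients will be followed-up up to five years")
- control rate of 3 to 10% per year
- margin and true rate ratio both 1.5, so that every rejection is an error
- one-sided 2.5%
- centre log-rate SD 0.3 (0 where stated)
- country log-rate SD 0.2, 0.3 or 0.5. Between countries one SD above and one SD below the mean, the rate ratio is exp(2 × SD) = 1.49, 1.82 or 2.72

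The share treated in a country with standardized log-rate u is 1/(1 + exp(c·u)). At u = +1 and −1 this gives:

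- c = 0.4: 40% and 60% (mild)
- c = 0.8: 31% and 69% (moderate)
- c = 1.3: 21% and 79% (strong)

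Both models are Poisson mixed models with random centre. One has country random, the other has it fixed. Covariates and matched clusters are left out. There were 2500 runs per scenario, so the Monte Carlo standard error is √(0.025 × 0.975/2500) = 0.3 points near 2.5%, and 0.7 points near 14%.

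Unless stated, the rows use four countries, 6% per year and country SD 0.3.

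| Scenario | Error, random | Error, fixed | Bias in log RR, random | Country variance estimated as zero |
|---|---|---|---|---|
| Equal shares in all countries | 2.6% | 2.6% | +0.006 | 16% |
| Shares 31/69, unrelated to rate | 2.6% | 2.8% | −0.002 | 15% |
| Shares 31/69, correlation 0.5 | 3.6% | 2.0% | −0.035 | 17% |
| Shares 21/79, correlation 0.5 | 6.2% | 2.9% | −0.061 | 18% |
| Mild, aligned, SD 0.2 | 4.0% | 2.5% | −0.035 | 45% |
| Mild, aligned | 4.2% | 2.2% | −0.039 | 17% |
| Moderate, aligned | 7.0% | 2.8% | −0.077 | 23% |
| Moderate, SD 0.2 | 7.2% | 3.0% | −0.078 | 49% |
| Moderate, SD 0.5 | 5.0% | 2.6% | −0.050 | 1% |
| Moderate, centre SD 0 | 7.8% | 2.6% | −0.092 | 19% |
| Moderate, 3 countries | 6.8% | 2.2% | −0.068 | 19% |
| Moderate, 5 countries | 7.8% | 3.0% | −0.096 | 22% |
| Moderate, 3% per year | 7.0% | 2.2% | −0.120 | 39% |
| Moderate, 10% per year | 7.5% | 3.0% | −0.058 | 11% |
| Strong, aligned | 14.0% | 2.6% | −0.137 | 31% |
| Strong, 3% per year | 12.4% | 3.2% | −0.198 | 51% |
| Moderate, opposite direction | 1.1% | 2.7% | +0.086 | 22% |

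A log bias of −0.077 multiplies the rate ratio by exp(−0.077) = 0.93, so a true 1.50 reads on average as about 1.39. With country fixed, the bias stays within about 0.01 in every scenario. At a nominal 5%, the base moderate scenario gives 12.6% random and 5.5% fixed.

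**Step 3: precision.** A separate and simpler simulation (502 patients, no centre effects, true rate ratio 1.30) gave an example standard error of 0.172 with country random and 0.174 with country fixed. The difference is 0.174/0.172 − 1 = about 1%.

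**The case against.** The inflation depends on a premise for which the protocol offers no data: that exposure share and residual CVE rate run in opposite directions across countries. The model already adjusts for CV history, diabetes, cholesterol, weight, hypertension, smoking, alcohol, age and gender, so the residual country differences may be smaller than assumed. Events are adjudicated centrally and blind (section 9.4) and ECGs are read centrally (section 9.3.3), which limits recording artefacts. Section 9.7.6 builds the secondary Cox model with and without stratification by regrouped centre and country. Matched clusters built on a score that includes country could absorb part of the problem, and the simulation omits them.

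Most of this stands as a limit on size, not as an answer. Adjudication cannot restore events that local practice never recorded, and changes in hypertension treatment remain local decisions. The stratified Cox model may reveal a discrepancy, but it does not correct the primary estimate. The sensitivity analysis listed for the primary model adds only a CV-history time covariate. Whether country enters the propensity score is properly left to the statistical plan and is not a fault of the protocol.

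**Conclusion.** The point holds as a conditional risk with a nearly free remedy. The final model in section 9.7.5 makes country random with four to five levels, in a comparison where nothing balances exposure within country. Where confounding favours the drug, the nominal 2.5% error becomes about 4% (mild), 5 to 8% (moderate) or 12 to 14% (strong). These figures rest on assumed country SDs, treatment shares, event rates, alpha and margin, without covariates or clusters. The size under the full planned model has not been tested.

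A reader might infer three stronger things that the documents do not support:

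- **That the country variance cannot be estimated.** It can. It is very imprecise, and it came out as zero in 1 to 51% of runs in which a true country effect existed.
- **That the study has three countries.** The text plans four to five; three is only the firm part of the list.
- **That the plan doubles the false-positive rate.** It does so only under aligned confounding. With no association the error is nominal, and in the opposite direction the test is conservative.

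**What to change.** In section 9.7.5, move country from the random to the fixed part and leave everything else as it is:

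`CVE ~ nCVE_b + Σ RF_i + gender + age + trt + country + Offset(log-exp) + {center | country} + {cluster}`

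Centre within country has enough levels to stay random. The matched cluster must stay, because it is the plan's main tool against treatment-selection bias. The sentence that lists the random factors should then name only centre and cluster.

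The cost is 3 degrees of freedom with four countries and 4 with five (2 if only three take part), with essentially no loss of precision. The change is best made before any outcome data are seen.

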9.3.7. Exposure and adherence to OZAWADE®

9.3.7.1. Treatment exposure

Exposure to OZAWADE® will be collected at inclusion and at follow-up visits (if not started at inclusion), with the date of prescription and the prescribed dose.

At each follow-up visit, dose modifications, treatment interruptions and permanent discontinuation will be collected. Reasons of changes will also be collected.

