For patients with prior CV history, the nCVE $_b$ covariate summarizes the CV history of the patient and was considered into the main model. For sensitivity purposes (a) the time passed between the first occurrence of

a CV event and the start of pitolisant treatment expected to estimate the CV event duration will be used as an added covariate in the model.

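### The protocol's one named sensitivity analysis uses a covariate that ends at the start of pitolisant, a date never-exposed controls do not have

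*Protocol*

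**What the plan says.** Protocol Section 9.7.5 sets the purpose of the primary analysis as to "demonstrate that OZAWADE® supplementation does not increase CV events compared with control (non-inferiority"). The model is a Poisson mixed model with a log-exposure offset. It contains the number of CV events before baseline (nCVE_b), risk factors, demographics, random country, centre and matched-cluster effects, and treatment: "The last fixed factor is the treatment (trt) binary effect (0=control, 1=pitolisant").

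Under Sensitivity Analysis, the text opens "For patients with prior CV history" and notes that nCVE_b already summarises that history in the main model. It then introduces a time interval whose starting point is the patient's earliest such event. Where the interval ends, and how it enters the model, is put this way: "CV event and the start of pitolisant treatment expected to estimate the CV event duration will be used as an added covariate". The item is lettered (a) and no (b) follows.

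The protocol gives no reference date for patients who never start pitolisant and no value for patients without a prior CV event. It does not restrict this analysis to treated patients.

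Section 9.3.7.1 bears on who has a start date: "Exposure to OZAWADE® will be collected at inclusion and at follow-up visits (if not started at inclusion").

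**The concern.** The covariate runs between two dates, and the second exists only for patients who start pitolisant. It is therefore defined by membership of one of the two groups being compared. A covariate of that kind cannot adjust a comparison between the groups: either it removes one group from the fit or it becomes entangled with the treatment term.

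Treatment is not randomised, and the protocol expects baseline imbalance and treats prior CV history as the key predictor. A finer measure of that history is a sensible sensitivity check on the non-inferiority conclusion. As written, the check cannot do that job, and it is the only one this protocol names for the primary comparison.

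**Working it through.** The plan gives no figure for this analysis, so there is none to reproduce. The question is whether the treatment effect can be estimated, and what happens if the undefined values are filled in.

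**Inputs from the protocol.** Treatment is coded 0/1, and the added covariate runs from first CV event to pitolisant start (both Section 9.7.5). "502 patients are planned to be recruited" (Section 9.1.1). Follow-up is five years (Section 9.1.2.1).

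**Assumptions not in the documents.** Equal groups of 502 / 2 = 251; 20%, 40% or 60% of patients with prior CV history; base rate 0.06 per year; log-rate slopes of 0.4 per prior event and 0.05 per year since the first event; true rate ratio 1. The model was reduced to intercept, nCVE_b, trt and the added covariate, with offset log(5) and no random effects. There were 400 simulated studies per scenario.

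**Step 1: literal fit on complete cases.** Only treated patients with prior CV history have a value, about 251 × share:

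| Prior CV history | Expected complete cases | In one simulated dataset | Controls kept | Columns | Rank |
|---|---|---|---|---|---|
| 20% | 251 × 0.2 = 50 | 46 | 0 | 4 | 3 |
| 40% | 251 × 0.4 = 100 | 102 | 0 | 4 | 3 |
| 60% | 251 × 0.6 = 151 | 149 | 0 | 4 | 3 |

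Every remaining row has trt = 1, so that column equals the intercept and the treatment effect is not estimable. This does not depend on the assumed rates or slopes.

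**Step 2: undefined values set to 0.** Let D be the time since the first CV event (0 if none) and s its log-rate slope.

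- True model: log rate = a + b·nCVE_b + 0·trt + s·D
- Covariate as filled: trt·D
- Fitted model: log rate = a + b·nCVE_b + t·trt + s·trt·D

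The part s·(1 − trt)·D, which belongs to controls with CV history, is left out. The intercept and nCVE_b absorb some of it, and t moves to compensate: below 0 if s > 0, above 0 if s < 0, unchanged if s = 0. Results with s = +0.05:

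| Prior CV history | Mean RR, no added covariate (SE of log RR) | Mean RR, filled with 0 (SE) | Mean RR, interval ended at a date both groups have (SE) |
|---|---|---|---|
| 20% | 0.999 (0.142) | 0.916 (0.157) | 0.997 (0.143) |
| 40% | 1.005 (0.127) | 0.854 (0.152) | 1.004 (0.128) |
| 60% | 1.006 (0.116) | 0.802 (0.148) | 1.005 (0.116) |

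Against a truth of 1, the filled version is low by 1 − 0.916 = 8.4%, 1 − 0.854 = 14.6% and 1 − 0.802 = 19.8%.

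**Step 3: does the sign of the slope matter?** A second simulation, with different assumed event counts and durations, gave filled-in rate ratios of 0.89, 0.83 and 0.75 at s = +0.05, and 1.05, 1.13 and 1.24 at s = −0.05, with no bias at s = 0. Ending the interval at inclusion and adding a history indicator gave 0.98 to 1.02 in all nine combinations of share and slope.

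**The case against.** The strongest defence is that the wording is a drafting slip. For patients exposed at inclusion, the prescribing decision precedes enrolment (Sections 9.1.1 and 9.2.2.1), so the start of pitolisant may be shorthand for baseline. Section 9.7 only summarises principles, Section 9.7.2 makes all included patients eligible for analysis, and Section 9.7.3.1 leaves missing-data strategy to the SAP. That may well be the intent. But the value for a never-exposed patient is undefined rather than missing, and the protocol has already fixed the anchor. An SAP that follows it inherits the fault, and one that repairs it departs from the protocol. How patients without CV history are coded is ordinary SAP detail and is not part of the complaint.

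A reader might infer more than the text supports:

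- *That the study cannot estimate its treatment effect.* The primary model in Section 9.7.5 does not contain this covariate.
- *That estimation fails however the model is run.* It fails under complete-case fitting. A fill-in rule gives a number, though a distorted one, and the protocol states no such rule.
- *That the distortion always favours pitolisant.* Its direction follows the sign of the covariate's effect, which the documents do not give.
- *That every control lacks a value.* This is strict only for never-exposed patients. Section 9.3.7.1 allows a later start; if late starters are analysed as controls they have a date, but one after inclusion.
- *That 251 controls are affected.* The equal split is an assumption, and Section 9.9 gives 195 per group. The argument needs neither count.
- *That no other sensitivity analysis will exist.* An unseen SAP may add some, and Section 9.7.6 provides Cox models, labelled secondary.

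**Conclusion.** The point holds for this one sensitivity model. Its covariate depends on a date that never-exposed controls cannot have, so the analysis as written cannot show whether a finer measure of CV history changes the non-inferiority conclusion. On complete cases the treatment effect is not estimable, whatever the event rates. With zero-filling, the treatment rate ratio was off by roughly 8% to 20% in the main simulation. Those sizes rest on assumed history shares, base rate and slopes and on a reduced model without random effects, so they illustrate the mechanism and do not predict this study's bias. The distortion disappears only if the covariate has no effect, in which case the analysis adds nothing. The sentence should be corrected, but the primary analysis does not depend on it.

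**What to change.** In Section 9.7.5, Sensitivity Analysis, replace the end of the interval. Define the covariate as the time from the first CV event before inclusion to the inclusion date, identically in both groups. Set it to 0 for patients with no prior CV event, and add a prior-CV-history yes/no indicator alongside nCVE_b. All patients then stay in the model, the covariate is a baseline quantity for late starters too, and the indicator stops the value 0 being read as an event on the day of inclusion.

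The text change is one sentence. The data cost is small but real: the date of the first prior CV event must be recorded at inclusion for both groups. The sponsor's own covariate already needs that date, but Section 9.3.2 lists prior CV conditions without explicitly asking for event dates, so an eCRF field may have to be added.
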